### **Patient preference of DT and iron chelation at Week 4 and Week 24**

The proportion and percentage (%) of patients including 95% CI will be reported separately for preference and non-preference of DT over iron chelation at Week 4 and Week 24. Exact and asymptotic p-values of Mc Nemar's test will also be presented as analogous to primary analysis, described in Section 2.5.2. The OR of patient preference (i.e.  $OR=p_{12}/p_{21}$ ), 95% CI and p-values will also be presented. Only patients who are pre-treated with iron-chelation will be considered.

**Reasons of patient preference**

The reasons or factors influencing behind patient preference of FCT over DT will be summarized at Week 28 and 48. The number and percentage (%) of patients for selecting each reason will be presented for preference of each study treatment. In addition to that, the summary of reasons behind non-preference of each study treatment will also be presented.

Similar summaries will also be provided for different preference comparisons at Week 4 and 24.

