7.3.1 Preference Questionnaire

The preference questionnaire is a four item questionnaire. There are four separate versions depending on the week(s) that the questionnaire is administered.

For week 48 (primary endpoint) the first item asks the patients (or parents of young patients from 2 to 9 years old) which medicine they are currently taking with the response options: "Tablet to dissolve in liquid", "Film coated tablet ", "Sprinkle powder on food" and "I don't know". The second item asks which of the medicines did the patient "Like best" with the same response options as that of the first item. Finally, the third item asks the patient why he/she preferred the medicine they chose.

For week 28 the first item asks patients to choose from the following medicines: “Tablet to dissolve in liquid”, “Film coated tablet (taken once a day)”, “Tablet (taken 3 times a day)”, “Sprinkle powder on food”, “Injection” and “I don’t know”. The second items remain the same asking which medicine the patients like the best (out of the above response options). Similarly the third item remains the same.

For weeks 4 and 24 the first item asks patients to choose from the following medicines: “Tablet to dissolve in liquid”, “Tablet (taken 3 times a day)”, “Injection” and “I don’t know”. The second items remain the same asking which medicine the patients like the best (out of the above response options). Similarly the third item remains the same.

The following preference attributes are provided:

- Taste
- Aftertaste (taste left in your mouth after you swallow)
- Convenience (it’s not a problem to take your medicine - administration)
- Number of pills
- No/Less side effects
- Can correctly prepare the medicine
- Easier to remember to take the medicine
- Number of times you have to take the medicine
- No/Less pain on the injection site
- Gain my personal time with family and friends
- Other _____

The questionnaire is administered at week 4, week 24, week 28 and week 48. No total score is calculated on the preference questionnaire. Each item will be scored as the proportion of patients who select each response option.

7.3.2 mSICT – patients greater or equal to 10 years old

The Modified SICT (mSICT) questionnaire consists of 15 items that represent 3 domains; Adherence, Preference and Concerns.

The adherence domain consists of 7 items, 6 of which are measured using a 5 point response scale.

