**Table 1.2.1: Study objectives and related endpoints**

| Objective   | Endpoint  |
|---|---|
| Primary  |   |
| To evaluate patient preference between deferasirox FCT and deferasirox DT | Proportion of patients claimed preference of deferasirox FCT over deferasirox DT as measured by preference questionnaire at Week 48 |

| Objective   | Endpoint   |
|---|--|
| Secondary  |  |
| To evaluate patient preference of deferasirox FCT or deferasirox DT or previous iron chelation                                      | Proportion of patients claimed preference of deferasirox FCT, deferasirox DT, and previous iron chelation as measured by preference questionnaire at Week 28   |
| To evaluate patient preference of deferasirox DT or previous iron chelation   | Proportion of patients claimed preference of deferasirox DT, over previous iron chelation as measured by preference questionnaire at Week 4 and Week 24  |
| To evaluate the reason behind preference for deferasirox FCT or deferasirox DT  | Proportion of preference reasons for deferasirox FCT over deferasirox DT as measured by preference questionnaire at Week 28 and Week 48  |
| To evaluate the effect of deferasirox FCT compared with deferasirox DT on patient compliance using pill count                       | Relative consumed pill count during deferasirox FCT (Week 25 to 48) compared with deferasirox DT (Baseline day 1 to Week 24)   |
| To evaluate the effect of deferasirox FCT compared with deferasirox DT or previous iron chelation on patient palatability using PRO | Absolute and relative change in domain scores of palatability questionnaire over time during deferasirox FCT (Week 28 to 48) compared with deferasirox DT (Week 4 to 24) or previous iron chelation (Screening)      |
| To evaluate the effect of deferasirox FCT compared with deferasirox DT or previous iron chelation on patient satisfaction using PRO | Absolute and relative change in domain scores of SICT questionnaire over time during deferasirox FCT (Week 28 to 48) compared with deferasirox DT (Week 4 to 24) or previous iron chelation (Screening)              |
| To evaluate the effect of deferasirox FCT compared with deferasirox DT or previous iron chelation on patient GI symptom using PRO   | Absolute and relative change in domain scores of SICT questionnaire over time during deferasirox FCT (Week 28 to 48) compared with deferasirox DT (Week 4 to 24) or previous iron chelation (Screening)              |

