### **Preference questionnaire**

The preference questionnaire is a three item questionnaire. There are three separate versions depending on the week(s) that the questionnaire is administered. Week 4 and 24 contains preference questions on DT and iron chelators, Week 28 contain questions on all three medications and Week 48 on DT and FCT only.

Summaries of the preference questionnaires will be performed at Visits 4, 24, 28 and 48, if data is available, in Core phase of the study and additionally from the data collected at the time of immediate next visit based on patients who had treatment switching. No total score is calculated on the preference questionnaire. Each item will be scored as the proportion of patients who select each response option.

The analysis of preference data has been explained in [Section 2.5](#) and [Section 2.7](#).

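### Week 28 reasons are labelled as reasons for FCT over DT, but the Week 28 form asks for the best of all chelators and names no comparator

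*SAP*

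**What the plan says.** **What will be reported.** SAP 2.7.2, under reasons of patient preference, states: "The reasons or factors influencing behind patient preference of FCT over DT will be summarized at Week 28 and 48". The layout follows: "The number and percentage (%) of patients for selecting each reason will be presented for preference of each study treatment". The endpoint in SAP Table 1.2.1 is "Proportion of preference reasons for deferasirox FCT over deferasirox DT as measured by preference questionnaire at Week 28 and Week 48". Protocol Table 3-1 and Protocol 10.5.2 say the same. None of these places treats Week 28 differently from Week 48, limits the patients, or gives the Week 28 reasons a label that is neutral about the comparator.

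**What is asked.** Protocol 7.3.1 introduces the Week 28 version with "For week 28 the first item asks patients to choose from the following medicines" and lists the dispersible tablet, the film-coated tablet, a tablet taken three times a day, sprinkled powder, injection and a don't-know option. Item 2 asks which of these is liked best. Item 3 is described under Week 48 ("Finally, the third item asks the patient why he/she preferred the medicine they chose") and is said to be unchanged at Week 28. SAP 2.11 confirms the difference in scope: "Week 28 contain questions on all three medications and Week 48 on DT and FCT only".

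**The concern.** The plan attaches a two-way label, FCT against DT, to answers from a question with several alternatives and no named comparator. For a patient whose only other experience is DT, the two come to the same thing. For a patient who has also taken deferoxamine or deferiprone, a reason for choosing FCT may be a reason against the earlier drug.

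Explaining why one deferasirox formulation is preferred to the other is a stated secondary objective. If the Week 28 table is produced as written, a reader could take an advantage over injections or three-times-daily tablets as an advantage over DT. Some such answers would look odd in the table. Others (taste, convenience, number of pills, side effects) would look entirely plausible, and nothing in the recorded data would show which comparator the patient had in mind.

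**Working it through.** The plan gives no figure for this point, so the check sets the form beside the label.

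1. **Form against label.**

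| | Week 28 | Week 48 |
|---|---|---|
| Medicines offered at item 2 | DT, FCT, three-times-daily tablet, sprinkled powder, injection | DT, FCT, sprinkled powder |
| Comparator named at item 3 | none | none |
| Label in SAP 2.7.2 and Table 1.2.1 | reasons for FCT over DT | reasons for FCT over DT |

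 The label fits the medicine options at Week 48. At Week 28 it is narrower than the question.

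2. **What the choice implies.** A patient who picks FCT as best of the list also likes it better than DT. The Week 28 preference count can therefore carry the FCT-over-DT label. The reasons cannot inherit it, because item 3 asks about the chosen medicine in general. The same holds for patients who pick DT at Week 28.

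3. **The reason list.** Protocol 7.3.1 gives 10 named reasons plus a free-text option, 11 in all. Two of the 10 cannot separate FCT from DT: the one on injection-site pain, since both are oral, and "Number of times you have to take the medicine", since both are taken once daily (Protocol 4.1 and Table 6-2). The list is given once for all versions of the form, so these two options are not shown to be confined to Week 28.

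4. **Who is affected.** Anyone who has taken another chelator. The SAP's own grouping does not isolate these patients: SAP 2.3.3 classes a patient as naïve if no chelation was received in the 6 months before study drug. Protocol 5.2 admits deferasirox-naïve patients, and footnote 10 to Protocol Table 7-1 mentions patients without chelation in the previous 6 months separately from naïve patients. The SAP's naïve group may thus include people who used injections or deferiprone earlier.

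5. **Size.** Let q be the share of Week 28 FCT choosers with an earlier chelator, and r the share of those who give a reason aimed at it. The affected share is q × r. The documents give neither value, so the ranges below are assumptions.

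| q | r = 10% | r = 25% | r = 50% |
|---|---|---|---|
| 25% | 2.5% | 6.2% | 12.5% |
| 50% | 5% | 12.5% | 25% |
| 75% | 7.5% | 18.8% | 37.5% |
| 100% | 10% | 25% | 50% |

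 The range is 2.5% to 50%, which shows only that the effect could be small or large.

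**The case against.** The case for leaving the plan alone has several parts.

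- *The table is laid out by chosen medicine.* SAP 2.7.2 presents each reason by preferred treatment, so the body of the table already shows reasons among patients who chose FCT. This stands, and it narrows the problem to the label and endpoint wording. It does not remove it, because both still say FCT over DT.
- *A split by chelation status already exists.* SAP 2.1 promises one wherever applicable. It would help, but it leaves the label on the pre-treated and total columns, and it uses the 6-month definition.
- *DT is the fresher comparison.* A patient who follows the schedule reaches Week 28 after 24 weeks of DT and about 4 weeks of FCT, with any earlier chelator stopped at least 5 days before Day 1. DT may well be foremost in mind. That bears on how often the problem occurs, not on whether the form settles it.
- *Week 48 is not watertight either.* Item 3 names no comparator there, and no separate reason list is shown for it. This stands: Week 48 is better because its medicine options are limited to deferasirox, but the two non-discriminating reasons need a flag there too.
- *The endpoint is descriptive.* SAP 2.7.2 rules out formal testing of secondary endpoints. This stands and limits the weight of the point.

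A reader might go further and infer that pre-treated patients' Week 28 reasons, as a class, are reasons against injections or three-times-daily tablets, or that the Week 28 preference for FCT over DT is itself inflated. The documents support neither. The reasons are ambiguous, not known to be misdirected, and the preference follows logically from the choice of FCT as best.

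**Conclusion.** The mismatch is real and is confined to the label on the reasons. At Week 28 the plan reports as FCT against DT a contrast that the form did not collect. For patients with any earlier chelator, the reasons may refer to that chelator. The Week 28 preference counts, the primary analysis at Week 48 and the sample size are unaffected.

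The size is unknown. The 2.5% to 50% range rests wholly on assumed values of q and r, and no single percentage within it should be cited as a finding. The conclusion itself needs only two things: that the Week 28 form is as Protocol 7.3.1 and SAP 2.11 describe it, and that patients who used other chelators are eligible, which both documents say. It is worth correcting because the objective is stated and the correction is cheap; it is not a threat to the trial's main result.

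**What to change.** In SAP 2.7.2:

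- Base the summary of reasons for FCT over DT on the Week 48 form.
- Title the Week 28 table *reasons for choosing FCT (or DT) as first choice among all listed chelators*, and split it by prior chelation.
- Keep an FCT-over-DT reading at Week 28 only for patients who have never taken another chelator. Do not use the 6-month naïve definition of SAP 2.3.3 for this. It assumes that the prior chelation history taken at screening reaches back beyond 6 months, which should be confirmed.
- At both weeks, footnote the injection-site-pain and dosing-frequency reasons as unable to separate two oral once-daily forms.

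**Cost.** Wording and a table split; no new data and no change to conduct. Fewer patients remain in the Week 28 FCT-over-DT table, while Week 48 keeps everyone who answered. Because Week 28 is part of the protocol endpoint, SAP section 4, which now reads as not applicable, should record the change. The SAP history shows a post-interim-lock addendum with the same date as the latest amendment, and that lock followed Week 48, so the entry should also say that the change was made after the Week 28 data were locked.

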**Compliance using pill count**

Compliance is measured by pill/tablet count based on amount of medication dispensed, returned and reported as lost/wasted by the patient or caregiver. Compliance will be calculated for each treatment (FCT: Week 25- Week 48, DT: Baseline day 1 – Week 24) as the ratio of total count consumed to total count prescribed, where total count consumed is derived from cumulative dispensed, returned and lost/wasted counts and total count prescribed is the cumulative prescribed count.

The prescribed count corresponds to the count prescribed by the investigator for a period that the patient should have taken during this period. For each strength (125 mg, 250 mg and 500 mg tablets for Deferasirox DT; 90 mg, 180 mg and 360 mg tablets for Deferasirox FCT), the prescribed count for a period is calculated from the daily prescribed count at the beginning of this period multiplied by the duration (days) of this period. The daily prescribed count is the sum of counts prescribed per strength. The duration of a period will be calculated as (end date of the period) – (start date of the period) + 1. The following period duration calculation will exclude the start day. The total count prescribed is the sum of counts prescribed over all periods.

If a patient does not return the study drug, the compliance will not be calculated.

Analysis of covariance (ANCOVA) will be performed for comparison between both treatment groups (FCT and DT). The ANCOVA model for compliance endpoint will include treatment group and age group (2 to < 6 years, 6 to < 10 years, 10 to < 18 years, and  $\geq$  18 years) and thalassemia transfusion dependence (TDT and NTDT) as factors. Least squares estimates, 95% CI and p-value will be presented for each treatment and difference between treatments.

Summary statistics of number of pills (and percentages) will also be presented overall and by treatment and subgroups.

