10.5.2 Other secondary efficacy objectives

The following secondary analyses will be performed:

Patient preference of FCT, DT, and iron chelation at Week 28

Proportion and percentage, % (and 95% CI) of patients with preference and non-preference of FCT over DT, FCT over iron chelation, and DT over iron chelation will be summarized separately at Week 28.

Homogeneity test (Cochran's Q test) may be performed to check the homogeneity of the three preferences. Exact and asymptotic p-values of Mc Nemar's test will also be presented as analogous to primary analysis, for each pair of treatment comparison. For comparison of FCT

and DT with iron-chelation, only patients who are pre-treated with iron chelation will be selected.

Patient preference of DT and iron chelation at Week 4 and Week 24

Proportion and percentage, % (and 95% CI) of patients with preference and non-preference of DT over iron chelation will be summarized at Week 4 and Week 24. Exact and asymptotic p-values of Mc Nemar's test will also be presented as analogous to primary analysis. Only patients who are pre-treated with iron-chelation will be considered.

Reasons of patient preference

The reasons or factors influencing behind patient preference of FCT over DT will be summarized at Week 28 and 48. Proportions of patients for selecting each reason will be presented for each study treatment. Further summary of reasons behind non-preference of each study treatment will also be presented.

Compliance using pill count

Compliance is measured by pill /tablet count based on amount of medication dispensed, returned and reported as lost/wasted by the patient or caregiver. Compliance will be calculated for each treatment (FCT: Week 25- Week 48, DT: Baseline day 1 – Week 24) as the ratio of total count consumed to total count prescribed, where

total count consumed is derived from cumulative dispensed, returned and lost/wasted counts;

- total count prescribed is cumulative prescribed count

Analysis of covariance (ANCOVA) will be performed for comparison between both treatment groups (FCT and DT). The ANCOVA model for compliance endpoint will include treatment group and age group ((2 to <6 years, 6 to <10 years, 10 to <18 years, and ≥ 18 years) and thalassemia transfusion dependence (transfusion and non-transfusion dependent) as factors. Least squares estimates, 95% CI and p-value will be presented for each treatment and difference between treatments.

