### **Treatment period**

The planned treatment duration of the core phase is 48 weeks (24 weeks of DT followed by 24 weeks of FCT) and the planned treatment period for the extension phase is another 48 weeks of FCT.

The total duration of the study is approximately 104 weeks (including the Screening, Treatment and Safety Follow-up visits).

Patients will be followed up for safety purposes for 30 days after the last dose of study drug (regardless if that situation occurs during core or extension phase).

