**Table 2-1 Contingency Table for Risk\***

|                          | Treatment |        |
|--------------------------|-----------|--------|
|                          | DFX FCT   | DFX DT |
| No of patient with AE    | FCTE      | DTE    |
| No of Patient without AE | FCTN      | DTN    |

\*separate calculation will be done for each SOC

$$\text{Risk difference (RD)} = \frac{FCTE}{FCTE+FCTN} - \frac{DTE}{DTE+DTN} = p_1 - p_2,$$

$$\text{where } p_1 = \frac{FCTE}{FCTE+FCTN} \text{ and } p_2 = \frac{DTE}{DTE+DTN}$$

The sampling distribution of RD is approximately normal.

$$\begin{aligned} \text{Hence, Standard Error for RD} = \text{SE( RD)} &= \sqrt{\frac{FCTE \cdot FCTN}{(FCTE+FCTN)^3} + \frac{DTE \cdot DTN}{(DTE+DTN)^3}} \\ &= \sqrt{\frac{p_1(1-p_1)}{N_1} + \frac{p_2(1-p_2)}{N_2}}, \end{aligned}$$

$$\text{where } N_1 = FCTE + FCTN \text{ and } N_2 = DTE + DTN$$

$$95\% \text{ CI of SE(RD)} = RD \pm 1.96 \times SE(RD)$$

In plot all results will be presented in percentages (%).

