### SAS code for ANCOVA

```
proc glm data = ;  
class treatmentgroups;  
model compliance = treatmentgroups agegroup thalassemiatransdep;  
run;  
quit;
```

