### Example SAS Code for Forest plot

```
%let gpath='C:\';  
%let dpi=200;  
  
data ae;  
input Pref $1-30 NA NB SNA SNB;  
datalines;  
ABDOMINAL PAIN 20 61 216 431  
ANOREXIA 2 15 216 431  
ARTHRALGIA 1 15 216 431  
BACK PAIN 10 23 216 431  
BRONCHITIS 8 11 216 431  
CHEST PAIN 9 12 216 431  
CHRONIC OBSTRUCTIVE AIRWAY 76 95 216 431  
COUGHING 13 26 216 431  
DIARRHEA 23 90 216 431  
DIZZINESS 9 29 216 431  
DYSPEPSIA 8 42 216 431  
DYSPNEA 15 9 216 431  
FATIGUE 4 16 216 431  
FLATULENCE 6 20 216 431  
GASTROESOPHAGEAL REFLUX 5 12 216 431  
HEADACHE 14 36 216 431  
HEMATURIA 2 14 216 431  
HYPERKALEMIA 4 9 216 431  
INFECTION VIRAL 12 26 216 431  
INJURY 12 30 216 431
```

|                            |    |    |     |     |
|----------------------------|----|----|-----|-----|
| INSOMNIA                   | 4  | 26 | 216 | 431 |
| MELENA                     | 7  | 12 | 216 | 431 |
| MYALGIA                    | 6  | 12 | 216 | 431 |
| NAUSEA                     | 10 | 82 | 216 | 431 |
| PAIN                       | 4  | 17 | 216 | 431 |
| RASH                       | 4  | 9  | 216 | 431 |
| RESPIRATORY DISORDER       | 4  | 11 | 216 | 431 |
| RHINITIS                   | 11 | 17 | 216 | 431 |
| SINUSITIS                  | 13 | 28 | 216 | 431 |
| UPPER RESP TRACT INFECTION | 33 | 68 | 216 | 431 |
| URINARY TRACT INFECTION    | 6  | 12 | 216 | 431 |
| VOMITING                   | 6  | 37 | 216 | 431 |
| WEIGHT DECREASE            | 2  | 9  | 216 |     |

run;

```
/*--Compute Proportions for treatment A & B, Mean and Risk--*/
```

```
data ae_risk;
```

```
  set ae;
```

```
  keep pref a b mean lcl ucl;
```

```
  a=na/sna;
```

```
  b=nb/snb;
```

```
  factor=1.96*sqrt(a*(1-a)/sna + b*(1-b)/snb);
```

```
  lcl=a-b+factor;
```

```
  ucl=a-b-factor;
```

```
  mean=0.5*(lcl+ucl);
```

run;

```
/*--Sort by mean value--*/
```

```
proc sort data=ae_risk out=ae_sort;
```

```
  by mean;
```

run;

```
/*--Add alternate reference lines--*/
```

```
data ae_ref;
```

```
  set ae_sort;
```

```
  if mod(_n_, 2) eq 0 then ref=pref;
```

run;

```
proc print;run;
```

```
/*--Create template for AE graph--*/
```

```
proc template;
```

```
  define statgraph AEbyRelativeRisk;
```

```
    dynamic _thk _grid;
```

```
    begingraph;
```

```
      entrytitle 'Most Frequent On-Therapy Adverse Events Sorted by Risk Difference';
```

```
      layout lattice / columns=2 rowdatarange=union columngutter=5;
```

```

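### The FCT–DT compliance comparison and the AE risk-difference interval treat the same patients as two independent samples, so their stated precision is right only if within-patient correlation is zero

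*SAP*

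**What the plan says.** **Design.** SAP 2.1.1 (Treatment period) describes the core phase as "24 weeks of DT followed by 24 weeks of FCT". SAP 2.7.1 puts secondary efficacy endpoints on the Full Analysis Set, and SAP 2.2 admits to that set only patients who took both formulations. The Safety Set needs a dose of either one. Protocol section 10 itself notes that a patient can be counted under more than one treatment group.

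**Compliance.** SAP 2.7.2 calculates one ratio per formulation period, then says "Analysis of covariance (ANCOVA) will be performed for comparison between both treatment groups (FCT and DT". The factors are treatment, age group and TDT/NTDT. Protocol 10.5.2 has the same model: "The ANCOVA model for compliance endpoint will include treatment group and age group", plus transfusion dependence. The promised output is: "Least squares estimates, 95% CI and p-value will be presented for each treatment and difference between treatments". The code in SAP 5.4.2 is PROC GLM with "model compliance = treatmentgroups agegroup thalassemiatransdep" and no subject, RANDOM or REPEATED term. Its CLASS statement lists only the treatment variable, and there is no LSMEANS statement. Some patients may have only one value: "If a patient does not return the study drug, the compliance will not be calculated".

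**AE risk difference.** Below Table 2-1, SAP 2.8.1 gives the standard error as the square root of p1(1−p1)/N1 + p2(1−p2)/N2, separately for each system organ class (SOC), states "The sampling distribution of RD is approximately normal", and sets limits at ±1.96 SE. The example forest-plot code does the same: "factor=1.96*sqrt(a*(1-a)/sna + b*(1-b)/snb".

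Neither document adds a patient effect, covariance term or paired method to either analysis.

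**The concern.** Two compliance ratios from one patient share that patient's habits, and two AE indicators from one patient share that patient's susceptibility. Both methods treat them as coming from different people. The plan recognises pairing elsewhere: the primary comparison (SAP 2.5.2) and the secondary preference comparisons (SAP 2.7.2) use McNemar's test.

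At stake is the precision reported for two between-formulation comparisons. If correlation is positive, the plan gives up precision that a within-patient design offers, and a real difference in compliance or tolerability could look inconclusive. If it is negative, the intervals claim too much precision.

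**Working it through.** **Inputs.** The only sizing figures are for the primary test (SAP section 3): discordant proportions 0.45 and 0.25, 80% power, two-sided 0.05, 130 patients at Week 48, 145 enrolled. They reproduce: (1.960 + 0.842)² × (0.70 − 0.20²) / 0.20² = 129.5, so 130; and 130 / 0.90 = 144.4, so 145. I borrow 130 and 145 as plausible counts. The documents give no correlation ρ, compliance SD, AE risk or age mix, so these are assumed and shown over a range.

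**1. Compliance difference, 130 complete pairs, equal variances.** The planned variance is 2σ²/n and the correct one is 2σ²(1−ρ)/n. The planned SE is therefore 1/√(1−ρ) times the correct SE, and the nominal 5% test has true level 2·P(Z > 1.96/√(1−ρ)). With σ = 10 points, the planned 95% half-width is 1.96 × 10 × √(2/130) = 2.4 points.

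| ρ | planned SE / correct SE | true level of 5% test | correct half-width (points) |
|---|---|---|---|
| −0.2 | 0.91 | 7.4% | 2.7 |
| 0 | 1.00 | 5.0% | 2.4 |
| 0.3 | 1.20 | 1.9% | 2.0 |
| 0.5 | 1.41 | 0.6% | 1.7 |
| 0.7 | 1.83 | under 0.1% | 1.3 |

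Simulating the model in the SAP text (40,000 trials per setting, three patient mixes) gave 7.3–7.5%, 5.0–5.2%, 1.9–2.0%, 0.6% and 0.04–0.06%. A paired test stayed at 4.8–5.2%.

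**2. AE risk difference, 145 on DT of whom 130 also take FCT, risks 30% and 20%.** Planned variance: 0.2×0.8/130 + 0.3×0.7/145 = 0.002679, so SE 5.18 points and half-width 10.1. The omitted term is 2ρ√(0.16×0.21)/145.

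- ρ = 0.3: 0.002679 − 0.000759 = 0.001921, SE 4.38, half-width 8.6, ratio 1.18.
- ρ = 0.5: 0.002679 − 0.001264 = 0.001415, SE 3.76, half-width 7.4, ratio 1.38.
- ρ = −0.1: ratio 0.96.

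In simulation at risks of 10–50%, the planned 95% interval covered about 98%, 99% and 94% respectively.

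**3. Per-treatment LS means.** For n pairs, true variance / model variance = [1 + nq(1+ρ)/2] / [1 + nq/2], where q measures how far the LS-mean weights lie from the observed patient mix. Suppose age group and TDT/NTDT are class factors, LS means weight the cells equally, the age mix is 5/10/25/60% and 90% are TDT, with age and TDT status unrelated. Then:

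- age part: 0.20²/0.05 + 0.15²/0.10 + 0 + 0.35²/0.60 = 1.23
- TDT part: 0.40²/(0.9×0.1) = 1.78
- nq = 3.01

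The variance ratio is 1.18 / 1.30 / 1.42 at ρ = 0.3 / 0.5 / 0.7, so coverage is about 93 / 91 / 90%. With LS means at the observed margins, or with groups of equal size, q = 0, the ratio is 1 and coverage is 95%. The SAP code as written enters age group and TDT/NTDT as numeric covariates. LS means then sit at the covariate means, and simulated coverage is again about 95%.

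**4. Sparse organ classes.** With the same 145/130 overlap and risks of 2% (DT) and 1% (FCT), the planned interval covers about 94% at ρ = 0.3 and 0.5. A Wald interval clustered on patient covers about 90% and 86%.

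**The case against.** The strongest reply is that this matters little. SAP 2.7.2 rules out formal testing of secondary endpoints, the forest plot in SAP 2.8.1 is discretionary, and under positive correlation, the likely case, both difference intervals err on the wide side. In the SD-10 example at ρ = 0.5 the cost is 2.4 against 1.7 points of half-width. This stands as a limit on the consequence, but the SAP still commits to a CI and p-value for compliance and writes out the AE interval.

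Three stronger readings are tempting, and the documents do not support them.

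- *A reader might infer inflated false-positive findings.* That needs negative within-patient correlation, for which neither document gives any ground. The true levels in the table describe a reported p-value, not a planned formal test.
- *A reader might infer that the per-treatment compliance intervals are generally too narrow.* That needs class factors, equal cell weights and an unequal mix together with positive correlation. The SAP states factors but no weighting, and its code as written does not produce the problem.
- *A reader might infer that a clustered interval is better in every organ class.* It is not where events are few, and SAP 2.8.1 chose the risk difference precisely because some DT counts may be zero.

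It is also fair to say that pairing may be incomplete: the Safety Set includes patients who never reach FCT, and compliance is not calculated where drug is not returned. This reduces the effect without removing it. The AE ratios above already allow for 15 unpaired patients.

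**Conclusion.** The point holds for the two between-formulation intervals and the compliance p-value. Their precision is correct only at zero within-patient correlation. With complete pairs the estimates themselves are unaffected. The sizes (1.20 / 1.41 / 1.83 for compliance at 0.3 / 0.5 / 0.7, and 1.18 / 1.38 for AEs at 0.3 / 0.5) rest on assumed correlations, equal compliance variances in the two periods, and counts borrowed from the sample-size section. Undercoverage of the per-treatment LS means is conditional on choices that the SAP leaves open. The primary McNemar analysis and the sample size are untouched. This should be corrected because it misstates reported precision; it does not threaten the trial's main conclusion.

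**What to change.** **Compliance.** Analyse the paired FCT–DT difference, or fit a repeated-measures model with patient as subject (REPEATED, unstructured), with formulation, age group and TDT/NTDT as class factors. State the LS-mean weighting and correct the CLASS statement. The repeated-measures model keeps patients with one usable period, but the gain is small. With SD 10 and 13 of 130 patients missing one period, half-widths at ρ = 0.3 / 0.5 / 0.7 are 2.12 / 1.80 / 1.40, against 2.16 / 1.83 / 1.41 for pairs only and 2.51 / 2.49 / 2.49 as planned.

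**AE risk difference.** Use a variance that recognises shared patients, such as GEE with identity link clustered on patient, which keeps patients who never took FCT. For organ classes with few events, use a score-type or small-sample paired interval, or show counts without a CI below a stated minimum.

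**Documentation.** The ANCOVA is also in Protocol 10.5.2, so declare the change in SAP section 4, now marked not applicable. The risk-difference formula is in the SAP only. The SAP's document history places its latest version after the interim lock, and SAP 2.14 schedules core-phase key efficacy and safety analyses at that lock. The new model is therefore post hoc for those data, and the planned ANCOVA should be reported alongside it. State also that pairing does not remove the confounding of formulation with period, since the planned order is DT first for every patient.

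**Cost.** No new data; modest extra programming and a short SAP amendment.
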